### **2.2 Study objectives**

For each of the five distribution models, the specific objectives are to use routinely collect programmatic data and qualitative data from the case studies to:

1. Describe, quantitatively, the process of distributing HIVST kits through each of the five distribution models;
2. Understand individuals' experiences of the different models of HIVST distribution;
3. Explore contextual factors likely to influence the acceptability of different models of HIVST to direct and secondary-distribution kit recipients. For example, at community level we will explore how availability of alternative HTS, anticipated and enacted stigma, and location of the distribution models influence people's choices. At interpersonal level, we will explore how power dynamics within a couple influence individuals' decisions.

4. Evaluate the frequency and nature of social harms associated with distribution of HIVST kits, and
5. Develop generalizable qualitative tools that can be used to evaluate different distribution models among key target populations

For four of the five models (all models except VMMC) we will also measure:

6. Costs, from the patient and the provider-perspective, of accessing and delivering HIVST kits, and those relating to linkage into confirmatory testing and care for individuals who self-test HIV-positive
7. The incremental cost-effectiveness of additional HIVST distribution models
8. Patient costs and their willingness-to-pay for HIVST

For the two secondary distribution models (implemented in ANC and HIV testing and treatment services), we will recruit a cohort (Secondary Distribution cohort) of index patients and their sexual partners (intended users of the HIVST kit) in order to investigate:

9. Factors associated with acceptance of HIVST for secondary distribution to index patients, with acceptance evidenced by accepting an HIVST kit(s) for onward secondary distribution.
10. Factors associated with the successful secondary distribution of HIVST to the sexual partners (the intended users of the secondary distribution HIVST kits) of index patients, as evidenced by the proportion of index patients who report that their primary partners used the HIVST kit within approximately 1-month of distribution
11. The proportion of intended users of the secondary distribution HIVST kit who report having accessed confirmatory testing, or HIV prevention or care services within approximately 3-months of distribution

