**Figure 2: Schematic of the quantitative and qualitative cohort in ANC and ART models**

For the secondary distribution cohorts, we will measure individual- and couple-level factors associated with acceptability to the index patient and intended user including: sex, age, previous HIV testing history, newly diagnosed or previously undisclosed HIV, relationship of the distributor and intended user (including type of relationship, age differential, measures of equality and empowerment), history of gender based violence and clinic from which the Index was recruited (ANC or HIV testing and treatment services).

The primary outcome of the secondary distribution cohorts is the:

- 1) Proportion of index patients who accepted an offer of secondary distribution HIVST kit(s) who report that their sexual partner(s) used the HIVST kit,

Secondary outcomes are the:

- 1) Proportion of index patients accepting an offer of HIVST kit(s) for secondary distribution,
- 2) Proportion of index patients who accepted an offer of a secondary distribution HIVST kit(s) who report that their partner used the HIVST kit(s) and linked to prevention or care services within 1-month of distribution

- 3) Proportion of intended recipients who self-report a) having used an HIVST kit and b) having attended confirmatory HIV testing, or HIV prevention or HIV care services within 3-months of distribution.

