## 5. Recruitment of study participants

---

All adults and adolescents aged 16 years or older (age of consent for HIV testing in Zambia) accessing HTS in clinics where HIVST distribution is being implemented are eligible for participation.

Specifically, individuals will be eligible to participate in data collection for the case studies if they:

- Are aged 16 years or older, and
- Able and willing to provide informed consent.

An individual is not eligible for participation in the study if they are:

- Under 16 years of age
- Unable and unwilling to provide informed consent
- Individuals not offered an HIVST kit, or
- If there is anything that, in the opinion of the investigator, would preclude informed consent or make study participation unsafe.

For the secondary distribution cohorts, participants are eligible if they meet these criteria and they are attending ANC or HIV testing and treatment services where secondary distribution of test kits is being offered. Informed consent will be sought for an exit interview and individuals who report accepting an offer of HIVST for secondary distribution to a partner will be eligible for a follow-up interview. Partners (intended users) of index individuals who collect an HIVST for secondary distribution will also be eligible for follow-up, providing consent is gained from the index individual at their follow-up interview and from the intended user.

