Approximately one-month after the offer of HIVST for secondary distribution, RAs will follow-up cohort participants who reported accepting an offer of an HIVST for secondary distribution, either at the health facility or in their homes or other convenient place. It is anticipated that a number of individuals who will accept the offer of HIVST secondary distribution may not return to the clinic on the appointment day for various reasons. Such individuals will be followed-up using a phone call or to their homes using the information provided during the exit interviews. A maximum of three (3) attempts on three different days through phone calls or home visit will be made. Individuals not answering the phone calls or not at home after three attempts will be considered lost-to-follow-up from the cohort.

To recruit the intended users of secondary distribution HIVST, individuals accepting a secondary distribution HIVST and who report that their partner (intended user) used the HIVST will be asked for permission to contact their partners, the intended users. For individuals who will give permission, the RA will either: (1) give the individual a card containing the RA’s contact details for the partner to call the RA or (2) ask the individual if they are willing to call their partner (intended user) to ask for permission to a) share their (intended user’s) phone number with the RA b) to introduce the RA to them (intended user). For intended users who will be willing to share their phone numbers or to talk to the RA, the RA will briefly introduce the study and obtain verbal permission. For intended users who will give verbal permission, the RA will obtain contact details and arrange to meet them. A maximum of three (3) attempts on three different days through phone calls will be made to contact or meet the intended user. RAs will arrange to meet the intended user at the clinic or at their home or any place provided it is safe and convenient for both the RA and the intended user. The intended user will also be provided with information about the study and asked to provide written consent before they are interviewed. The follow-up surveys for the distributor of the secondary distribution HIVST

and the intended user of the HIVST will focus on usage of the collected HIVST and linkage to care or HIV prevention services including their costs of accessing HIVST and linkage to HIV services as well as their willingness to pay for HIVST.

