### **7.3 Quantitative secondary distribution cohort data**

For the quantitative data arising from the secondary distribution cohorts, we will conduct analyses separately for the ANC and HIV testing and treatment cohorts. We will use descriptive analyses to describe the proportion of individuals accepting an offer of HIVST and the proportion who report that their partner used the HIVST. We will use standard logistic regression adjusting for study site to explore factors associated with accepting an offer of HIVST and with reported use of the HIVST.

Although the index individuals will be asked about linkage to care at 1-month follow-up, we will measure linkage to care using data from the intended users followed-up within 3-months after distribution. Linkage will be measured as the number of individuals reported to have linked to care (defined as accessing confirmatory testing services or attending an HIV care clinic for HIV-positive individuals or accessing VMMC services for HIV-negative males) among those who reported use of the HIVST.

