Demo 11a	How would you describe your relationship with this sexual partner?	Husband/wife (married or living as married); Boyfriend/girlfriend; casual partner; One-time partner	1; 2; 3; 4
Demo 12	Did you come alone to the facility or you came with your partner	Alone; With my partner	1; 2

Section 3: Use of HIVST kit			
Use_ HIVST-_IU 1	Did you receive an HIV self-testing kit from your partner?	No; Yes	0;1
Use_ HIVST-_IU 2	Before your partner gave you the HIVST, had you ever heard of HIV self-testing?	No; Yes	0;1
Use_ HIVST-_IU 3	Before your partner gave you the HIVST, had you ever used an HIV self-test?	No; Yes	0;1
Use_ HIVST-_IU4	When did you receive an HIVST from your partner?	MMYYYY	
Use_ HIVST-_IU5	Did you use the HIVST kit?	No; Yes	0;1
Use_ HIVST-_IU 6	If you did not use the test kit, what are some of the reasons why you did not? Please tick all that applies	Too busy; did not know how to use; feared getting the results; already	

		know my HIV-positive status	
Use_HIVST_IU 7	When did you use HIVST kit? If you can't remember please give your best guess	Year; month; day	
M_HIV_Test_IU 8	If you don't mind, what was the result of your HIV test using the test kit that you were given by your partner?	Reactive; non-reactive/negative; I don't know; I can't disclose	1; 2; 3; 4
Section 4: History of HIV testing			
H_HIV_Test_IU 1	I would like to ask you questions about your history of HIV testing. [if you used an HIVST from your partner, this is the time before you received the HIVST kit from your partner]		
H_HIV_Test_IU 2	Before receiving an HIV self-testing kit from your partner, had you ever tested HIV?	No; Yes	0;1
H_HIV_Test_IU 3	Please indicate yes to the following statements if they indicate the reasons why you have never tested for HIV and no if they do not  I have never tested for HIV before because:	No; Yes	0;1
H_HIV_Test_IU 3.1	I am not at risk of being HIV positive	No; Yes	0;1
H_HIV_Test_IU 3.2	I do not want to know my status	No; Yes	0;1
H_HIV_Test_IU 3.3	I'm afraid of testing positive	No; Yes	0;1
H_HIV_Test_IU 3.4	I'm afraid of stigma and discrimination from testing for HIV	No; Yes	0;1
H_HIV_Test_IU 3.5	My partner won't let me test	No; Yes	0;1

H_HIV_Test_IU 3.6	Other family won't let me test	No; Yes	0;1
H_HIV_Test_IU 3.7	I do not have money to test	No; Yes	0;1
H_HIV_Test_IU 3.8	I cannot take time off work to test	No; Yes	0;1
H_HIV_Test_IU 3.9	It's not a dignified thing to do at my age	No; Yes	0;1

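### Section 5.2 approaches a partner only after the index patient reports that the kit was used, so secondary outcome 3a measures confirmation of that report and not use among intended recipients

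*Protocol*

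**What the plan says.** **Recruitment rule.** Section 5.2 deals with index patients at the follow-up interview, about one month after distribution: "individuals accepting a secondary distribution HIVST and who report that their partner (intended user) used the HIVST will be asked for permission" to contact the partner. It gives no route to a partner whose index patient reports non-use or does not know.

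**Eligibility.** Section 5 has no such condition: "Partners (intended users) of index individuals who collect an HIVST for secondary distribution will also be eligible for follow-up", provided the index patient agrees at the follow-up interview and the partner consents.

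**Outcome.** Section 4.3.2 lists as secondary outcome 3 the "Proportion of intended recipients who self-report a) having used an HIVST kit and b) having attended confirmatory HIV testing", or prevention or care services, with a 3-month horizon. The same section says that partner follow-up is meant to measure use as well as linkage. The intended-user questionnaire in Appendix 3 asks whether the kit was received and used, and then: "If you did not use the test kit, what are some of the reasons why you did not".

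**Linkage.** Objective 11 in section 2.2 (and in the Summary) is "The proportion of intended users of the secondary distribution HIVST kit who report having accessed confirmatory testing, or HIV prevention or care services". Section 7.3 says "we will measure linkage to care using data from the intended users followed-up within 3-months after distribution" and takes the proportion "among those who reported use of the HIVST". Section 7.4 instead has linkage rest chiefly on what the index individual reports.

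**The concern.** To be asked about use, a partner must already have been reported as a user. Three groups are never approached: partners whose index patient reports non-use (including those never handed the kit), partners whose index patient does not know, and partners who first use the kit after the one-month interview, although outcome 3 runs to three months.

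A figure for 3a obtained this way says how often partners confirm an index report. It does not say how many intended recipients used the kit. The study is meant to inform scale-up and guidelines, and a high 3a could be read there as reach. Partners who were not interviewed cannot be recovered after fieldwork. The linkage wording adds to the problem, because the objective, the outcome list and the analysis section do not share a denominator or a main data source.

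**Working it through.** **Inputs, all from section 5.4:** about 300 per cohort needed; up to 30% lost; about 450 recruited; reported use 60% with the key factor and 40% without it.

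**The plan's own figures.** For 60% against 40% at a two-sided 5% level (sidedness is not stated), 300 gives 80.0% power with a 20:80 split of the factor and 93.8% with an even split. So at least 80% holds for splits between those limits. Allowing for loss, 300 / (1 - 0.30) = 429, which the protocol rounds up to about 450. Expected re-interviews: 450 x 0.70 = 315 per cohort. The stated sample size is consistent with its inputs. No figure is given for the partner outcomes.

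**Partners excluded by the rule.** Let f be the share with the key factor. Index-reported use is u = 0.6f + 0.4(1 - f), which lies between 0.40 and 0.60.

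| u | Can be approached, 315u | Never approached, 315(1 - u) |
|---|---|---|
| 0.40 | 126 | 189 |
| 0.60 | 189 | 126 |

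The second column is an upper limit, because index permission and partner consent are still needed. The third column counts every partner without an index report of use, not only those who received a kit and left it unused.

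**What 3a estimates under the rule.** Among partners approached, expected self-reported use equals the share of index reports of use that the partner confirms, if permission and consent are unrelated to confirmation. The protocol gives no value for that share. Two assumed routes:

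- *Direct agreement of 80-100%:* 3a reads 80-100%. Following all partners, with no use missed by the index patient, would give u x agreement, from 0.40 x 0.80 = 32% to 0.60 x 1.00 = 60%.
- *Index report treated as a test of true use t, with sensitivity se and specificity sp:* 3a = t·se / [t·se + (1 - t)(1 - sp)].
  - t = 0.4, se = 0.90, sp = 0.80: 0.36 / (0.36 + 0.12) = 75%
  - t = 0.5, se = 0.95, sp = 0.90: 0.475 / (0.475 + 0.05) = 90%
  - t = 0.6, se = 0.95, sp = 0.95: 0.57 / (0.57 + 0.02) = 97%

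The three denominators (0.48, 0.525, 0.59) are the index-reported use that these assumptions imply, and all lie within the protocol's 40-60%. Taken together, 3a would read about 75-100% when use is about 40-60%.

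**Linkage.** Let L be linkage among users.

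- *Section 7.3 denominator (reported users):* L with or without the rule, a factor of 1.0.
- *Intended users or recipients (objective 11, outcome 3b):* the true proportion is u x L if index reports are accurate and non-users do not link. The restricted sample shows L, which is too high by 1/u: 1/0.60 = 1.67 to 1/0.40 = 2.5. With an assumed L of 30%, 12-18% of all recipients would read as 30%. Any linkage among non-users makes the factor smaller.

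**The case against.** **The primary outcome and power are untouched.** This stands. The primary outcome is index-reported use among acceptors, and the sample size rests on it. Partner follow-up is stated as an aim, and section 5.4 calls the linkage results descriptive and unpowered. That limits the severity. It does not rescue 3a, since a descriptive proportion is exactly what selection distorts.

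**Linkage is already defined among users.** This stands too. A reader might infer that the partner-level linkage estimate is inflated; under the section 7.3 definition, leaving out non-users does not inflate it. Users missed by the rule might link differently, but the documents give nothing with which to size that.

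**The result is not fixed at 100%.** A reader might infer that 3a is close to 100% by construction. The documents do not support that. It depends on agreement between index and partner, for which they give no figure, and plausible assumptions go down to 75%.

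**Non-use is partly observed elsewhere.** Index patients report non-use and why a kit was not handed over, and the qualitative partner guide asks about refusal. The non-use items in the partner questionnaire could also serve when a partner contradicts the index patient, so they do not by themselves prove that the restriction is an error. The conflict with section 5 and with the stated purpose in section 4.3.2 remains.

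**Contacting more partners may carry risk.** Section 10.2 treats violence and coercion as serious risks of secondary distribution. The protocol does not give safety as the reason for the rule, but the sponsor may weigh it, and that is a fair reason to prefer relabelling.

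**Conclusion.** The concern holds in a limited form. Under section 5.2, outcome 3a is not a use rate among intended recipients; it is partner confirmation of an index report of use. The count of 126-189 partners per cohort never approached follows from the protocol's own planning figures. The 75-100% reading against true use of 40-60% rests on assumed agreement, sensitivity and specificity. The 1.7 to 2.5 times overstatement applies only to linkage read over intended users or recipients, and needs accurate index reports and no linkage among non-users.

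This should be fixed, but it does not threaten the study's main result. The one-month recruitment rule, the eligibility text, the outcome list and the linkage definitions need to agree.

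**What to change.** Reconcile sections 5 and 5.2 in one of two ways.

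1. **Drop the use condition.** Seek permission to contact the partner from every re-interviewed index patient who accepted a kit, whatever is reported about use, and keep index permission and partner consent as they are. This matches section 5. It costs one changed sentence in section 5.2 and more partner contacts: at most 126-189 further approaches per cohort before permission and consent. If contact is limited to partners who were handed the kit, name the denominator *partners given the kit*; that version is still narrower than section 5 and than all intended recipients.
2. **Keep the condition and relabel.** Call 3a partner confirmation of index-reported use, and state that no partner-reported use rate is estimated. Align the eligibility text in section 5 and the purpose in section 4.3.2. This costs wording only, but gives up a partner-reported use rate.

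In either case, state one linkage denominator (reported users, as in section 7.3) and one main linkage data source, and carry both through the Summary and sections 2.2, 4.3.2, 7.3 and 7.4. The choice must be made before partner follow-up starts.

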### **5.3 Recruitment of costing study participants**

For costing and willingness to pay studies, recruitment of study participants will follow the same procedure as for the qualitative and quantitative studies. Participants will be recruited as they exit their clinical consultation at ANC or HIV testing and treatment services. The costing study will focus on assessing client's costs of accessing HIVST and linkage to HIV services as well as their willingness to pay for HIVST.

In total 150 interviews will be conducted for both costing and willingness to pay data collection, 42 from participants in IDIs, 12 from qualitative cohort and 46 with users and intended users who will not be recruited in other studies. Costing study will only be done for community-led, work places, ANC and ART distribution models.

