## **4.2 Qualitative methods**

Qualitative data collection will begin with implementation of participatory activities through community consultation processes and stakeholder discussion, followed by IDI, FGD, mapping, and observation of HIVST distribution (Table 2). Qualitative data will provide understanding of contextual factors that mediated people's choices and behaviour. The qualitative research will explore the following themes:

1. Social support and social networks (friends, workmates, church, customs, support after testing, attitudes of HCWs)
2. Livelihood options
3. Knowledge of HIV testing and HIVST, and individual attitudes towards HIV testing and HIVST
4. Power relations, social harms and gender-based violence within couple/partners
5. Social effects of HIVST including stigma
6. Location and lay-out of distribution points, including community social and physical features
7. Environmental factors (flooding, disease outbreaks, strikes etc.)
8. Promotion and social marketing

A total of 12 FGDs and 46 IDIs will be conducted (see table 2 for distribution). Both the FGDs and IDIs will be conducted by trained RAs with the help of a Junior and senior social scientist. The Neighbourhood Committee (NHC) members will help to identify appropriate venues within the community. The NHC is a community-based organisation created by an act of parliament to ensure community involvement in the management of health related programmes in the community. The size of the focus groups will be between 8-12 participants. This is the recommended size to ensure interaction between the participants. Focus group discussion and IDI participants will be selected purposively for each distribution model, aiming for a range of ages, men and women, and individuals who accepted or declined an offer of HIVST. The composition of the FGDs is described in section 5.1 (recruitment of qualitative study participants). In addition 4 stakeholder discussions with representatives of community based groups and 15 observations of the mechanisms of distribution and interactions between distributors and clients will be conducted.

Twelve individuals from each of the quantitative cohorts linked to secondary distribution methods (24 in total) will be purposely selected to take part in the Secondary Distribution qualitative cohort. They will be interviewed at two points: at recruitment and follow-up.

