### 5.1 Recruitment of qualitative study participants

In total 46 IDIs, 12 FGDs, 4 stakeholder meetings and 15 observations will be conducted. The 42 IDIs will be conducted with purposefully selected individuals accessing VMMC (6), facility/ community-led (6), work places (6) ANC (12) HIV+ individuals (12) and health care workers (4). The 12 FGDs will be conducted with purposely selected community members to obtain community perspectives on the different models; 4 for the ANC model, 4 for HIV+ individuals' model, 1 for VMMC model, 2 for facility-led/community-led model and 1 for the workplace model. Of the 4 FGDs for the ANC model, 2 will be composed of individuals attending the ANC at the clinic and the other 2 of ordinary community members (women) recruited from the community. Similarly, the 4 FGDs for HIV+ will be divided into 2 (mixed sex) for individuals attending ART recruited from the clinic and the other 2 ordinary community members (mixed sex) recruited from the community. The VMMC and work place FGDs will be composed of individuals about to undergo VMMC and staff of work place. Stakeholder meetings will be conducted with representatives of different groups identified during community consultations. The four HCWs who are involved in distributing HIVST will be purposely selected (to ensure a

mix of gender and type or aspect of the model they are involved in) to take part in qualitative interviews. They will be asked for their perspectives on HIVST and the distribution models, linkage to care and prevention services, social harms and sustainability of the models. The study will be explained to them and consent obtained before taking part in the study. Other HCWs may take part in stakeholder meetings at the beginning of the study if the clinic/ HCWs are identified as key stakeholders in HIV care and prevention activities in the community.

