Twelve individuals (6 from the ANC and 6 from HIV+ individuals) recruited in the secondary distribution cohort will be purposively selected to participate in the qualitative cohort to explore the contextual factors affecting secondary distribution HIVST in ANC and through HIV-positive individuals. Individuals selected to participate in the cohort must have self-tested, and accepted secondary distribution on behalf of their partner. Using purposeful sampling, age, and gender will be taken into account to ensure a fair distribution of participants. Qualitative research assistants will spend extended times in the homes of the participants, using the rapport created to generate detailed data on participants' experiences with HIVST and particular the secondary distribution models. Such an ethnographic approach does not necessarily require many participants. RAs will inform quantitative cohort participants that they may be approached by researchers conducting qualitative research and asked to enrol in a qualitative cohort and that they will be asked to consent for this activity. Qualitative RAs will then approach the 12 individuals selected for the qualitative cohort and schedule interviews with them within 5 days. Follow-up interviews will be conducted immediately after the follow up visit for the quantitative cohort interviews. A key aspect of the qualitative cohort will be the extended contact with participants by the researchers in the participants' preferred milieu while at the same time conducting participatory research activities. The rapport created will be critical for prompting participants to share their experiences.

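### Section 5.3 states 150 costing and willingness-to-pay interviews, but its parts total 100, include VMMC clients excluded from costing, and probably count the qualitative cohort twice

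*Protocol*

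**What the plan says.** The costing sample is set in section 5.3: "In total 150 interviews will be conducted for both costing and willingness to pay data collection, 42 from participants in IDIs, 12 from qualitative cohort". The third and last source listed there is a group of 46 people taken from outside the other study components. The same section limits the models: "Costing study will only be done for community-led, work places, ANC and ART distribution models". Section 2.2 likewise leaves VMMC out of the cost objectives, and Table 2 marks its economic component as not applicable because it has already been costed.

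Section 5.1 gives the make-up of the in-depth interviews (IDIs): "accessing VMMC (6), facility/ community-led (6), work places (6) ANC (12) HIV+ individuals (12) and health care workers (4".

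The qualitative cohort has two sizes. Section 4.2: "Twelve individuals from each of the quantitative cohorts linked to secondary distribution methods (24 in total) will be purposely selected". Section 5.2: "Twelve individuals (6 from the ANC and 6 from HIV+ individuals) recruited in the secondary distribution cohort will be purposively selected".

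On recruitment, section 5.3 first adopts the procedures of the qualitative and quantitative studies and then adds: "Participants will be recruited as they exit their clinical consultation at ANC or HIV testing and treatment services".

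**The concern.** A stated sample size should equal the sum of its sources, and each source should consist of people who belong in the analysis. Here the sum fails. One source appears to contain clients of an excluded model, and another appears to be part of the first.

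Patient cost and willingness to pay are objectives 6 and 8, and section 7.4 plans a Tobit model of cost predictors. For the ANC and ART models other client cost data are planned. For the community-led and workplace models, the economic column of Table 2 lists document reviews, process data, observations and a costing abstraction sheet, with no client interviews. The section 5.3 sample is therefore the main planned source of client costs for those two models. As written, nobody can tell how many such clients will be interviewed.

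**Working it through.** **1. The total.** Inputs from section 5.3: 42, 12 and 46.

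- 42 + 12 + 46 = 100, against 150 stated.
- Gap: 150 − 100 = 50, and 50/150 = 33%.
- If the 150 is right and the last part is the misprint, that part would have to be 150 − 42 − 12 = 96.

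**2. Where the 42 comes from.** The section 5.1 list gives 6 + 6 + 6 + 12 + 12 + 4 = 46. Section 5.1 opens with 46 IDIs, then speaks of 42 while listing all 46. The only group whose removal leaves 42 is the 4 health care workers: 46 − 4 = 42. So the 42 appears to be all client IDIs: VMMC 6, facility/community-led 6, workplace 6, ANC 12, HIV-positive 12.

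**3. VMMC.** Removing the excluded model leaves 42 − 6 = 36.

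**4. Overlap.** Table 2 builds the same 46 as 18 + 24 + 4: 18 IDIs for the first three models, 24 for the qualitative cohort, 4 for health care workers. The 42 is then 18 + 24, and the 24 are the cohort's own interviews. The further 12 attributed to that cohort are therefore probably inside the 42 already.

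**5. Cohort size.** It is 24 people in section 4.2 and 12 in section 5.2. Table 2 can be read either way: one column gives 12 participants with 24 IDIs, another gives 12 individuals for each of the two models.

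**6. Resulting counts.**

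| Reading | Others = 46 | Others = 96 |
|---|---|---|
| Parts as listed | 42 + 12 + 46 = 100 | 42 + 12 + 96 = 150 |
| VMMC out, the 12 kept as additional | 36 + 12 + 46 = 94 | 36 + 12 + 96 = 144 |
| VMMC out, cohort once, 24 people | 6 + 6 + 24 + 46 = 82 | 6 + 6 + 24 + 96 = 132 |
| VMMC out, cohort once, 12 people | 6 + 6 + 12 + 46 = 70 | 6 + 6 + 12 + 96 = 120 |

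Section 5.3 names community-led but not facility-led. If all 6 facility/community-led IDIs came from the facility side, the last two rows would fall by 6, to 64–76 and 114–126.

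**7. Community-led and workplace.** The identifiable respondents are 6 + 6 = 12 IDIs, plus an unstated share of the 46.

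**The case against.** Several things can fairly be said for the plan.

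- **Interviews are not people.** Section 5.3 counts interviews, and cohort members are interviewed more than once (two points in section 4.2, three in the Summary). The 12 could be repeat interviews. This stands as a possibility, which is why the overlap is called probable. It does not help the sum: the listed parts still total 100.
- **The 42 is inferred.** The protocol never says that it is the client IDIs. The inference is strong because no other split of the section 5.1 list gives 42, but it remains an inference.
- **VMMC is not treated uniformly.** The Summary lists the cost objectives for all models, and the individual-cost tool in Appendix 5 is headed for all models. Sections 2.2 and 5.3 and Table 2 exclude VMMC, so this is one more inconsistency to settle.
- **Other cost data exist.** Under section 5.2 the follow-up surveys of index patients and intended users also ask about access costs, linkage costs and willingness to pay, and Table 2 lists exit interviews and the cohorts (about 450 each) as economic sources. A reader might infer that objectives 6 and 8 rest wholly on the section 5.3 sample. For ANC and ART they do not.
- **Recruitment routes exist.** A reader might infer from the sentence on clinic exits that community-led and workplace users cannot be reached. The documents do not support that: section 5.3 also adopts the qualitative procedures, and section 5.1 recruits at distribution points, in the community and at workplaces. What remains is a sentence narrower than the procedure it sits beside.
- **No precision target is stated.** It is tempting to express the shortfall as wider confidence intervals overall or per model. Section 5.3 gives no precision basis for 150 and no split by model, so such figures would measure no planned loss.

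**Conclusion.** The stated sample size is wrong as written: 150 against listed parts of 100. The document does not show which number is in error. Changing 46 to 96 would repair the sum but not the sample, since 6 VMMC clients would still be included and the cohort would probably still be counted twice.

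Distinct respondents in costed models are about 70–82 if the 46 is right and about 120–132 if it should be 96. These ranges assume that the 42 is the client IDIs, that the 12 overlap with them, and that the cohort is 12 or 24 people. If the 12 are separate, the counts are 94 and 144. Every one of these readings falls below 150. The figures describe the section 5.3 sample, not all cost data in the study.

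The point is moderate. It bears mainly on client costs in the community-led and workplace models. It does not touch the primary outcome of the secondary distribution cohorts or their sample size in section 5.4.

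**What to change.** In section 5.3:

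- Restate the total so that it equals its parts.
- Take out the 6 VMMC IDIs, and bring the Summary and Appendix 5 into line on whether VMMC clients are costed.
- Count the qualitative cohort once, or say that the 12 are repeat interviews of people already counted.
- State the number expected for each costed model: community-led, workplace, ANC and ART.
- Reconcile the sentence naming only ANC and HIV service exits with the distribution-point and workplace recruitment in section 5.1.

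Use one qualitative cohort size in section 4.2, Table 2 and section 5.2, and correct the 42 against 46 in section 5.1.

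If the total is restated downwards, the cost is protocol wording and a smaller stated sample. If 150 distinct eligible respondents are wanted, the additional users would have to number 150 − (6 + 6 + 24) = 114 with a cohort of 24, or 150 − (6 + 6 + 12) = 126 with a cohort of 12. That is real extra fieldwork compared with 46.
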